8.9.2.1. Documentation of the event

The investigator must ensure that all events are well documented. He/she should provide the sponsor on request, with anonymized copies of relevant documents (e.g. autopsy report and terminal medical reports [ICH E6 R2]).³⁵

8.9.2.2. Follow-up of adverse events

The investigator must ensure that follow-up of the participant is appropriate to the nature of the event, and that it continues until resolution if deemed necessary.

Any change in terms of diagnosis, intensity, seriousness, measures taken, causality or outcome regarding an AE already reported must be written up in a new complete evaluation of the event documented on the “Adverse event” page previously created for the event.

If the AE has not resolved at the participant's final visit, the participant must be followed up suitably and any information on the outcome of the event will be noted on the “Adverse Event” page previously created for the event.

If the follow-up of the participant is not done by the investigator him/herself (hospitalisation, followed by a specialist or the participant's general practitioner, ...), the investigator will do everything to establish/maintain contact with the person/department in charge of follow-up of the participant.

8.9.2.3. Special situations (pregnancy, overdoses, intake of IMP/NIMP by a person around the participant)

Pregnancy

If a female participant in the study becomes pregnant, the investigator must:

- Stop immediately the study treatments.
- Report it on an “Adverse Event” page as well as on the specific paper pregnancy form (1st page) to be notified immediately (ERIN).
- Contribute to the follow-up of this pregnancy and provide the sponsor with information concerning this follow-up (notably using the 2nd page of the specific paper pregnancy form).

If the partner of a participant becomes pregnant during the study, the pregnancy should not be reported in the e-CRF. The investigator should **immediately** contact the sponsor (contact details provided in the investigator's study file) who will inform him/her about the procedure to be followed.

Overdose of IMP or NIMP

- In case of overdose, the investigator should report it on an “Adverse Event” page to be notified immediately (ERIN).
- Overdose should be followed-up to ensure that the information is as complete as possible with regards to:
 - Dose details (number of units, duration, ...) and, if multiple overdose, details regarding other medicinal products or substance.
 - Context of occurrence, *i.e.* intentional (suicide attempt, other reason) or accidental (error in prescription, administration, dispensing, dosage).
 - Related signs and symptoms (“No related adverse events” to be reported otherwise).
 - Outcome.
- Insofar as possible, a blood sample should be collected for assay of the IMP taken.

Intake of IMP or NIMP by a person around the participant This event should not be reported in the e-CRF. The investigator should **immediately** contact the sponsor (contact details provided in the investigator's study file) who will inform him/her about the procedure to be followed.

8.9.2.4. Recording Methods in the e-CRF

Adverse events must be documented on the “Adverse Event” page of the e-CRF.

In case of chronic disease:

- If the disease is known when the participant enters in the study, only worsening (increased frequency and/or intensity of the episodes/attacks) will be documented as an adverse event.
- If a disease is detected during the study and if repeated episodes enable diagnosis of a chronic disease, the episodes will be grouped on the “Adverse Event” page previously created for the event which will clearly describe the diagnosis.

8.9.2.5. Procedure for an event requiring an immediate notification

In case of an event requiring an immediate notification, the investigator must:

- **Immediately** after being informed of this event, **fill in the participant's medical file** as well as the “**Adverse Event**” page of the e-CRF according to the general instructions available in the e-CRF, without waiting for the results of the clinical outcome or of additional investigations. When data will be submitted into the e-CRF system, an e-mail will be immediately and automatically sent to the sponsor.
- Fulfil his/her regulatory obligations to the Competent Authorities and/or to the IRB/IEC, in accordance with local regulations.

Moreover, on request, the investigator should provide the sponsor with the documents required in [Section 8.9.2.1](#).

If an adverse event initially non-serious worsens and becomes a serious adverse event, this must be reported **immediately** on an “Adverse event” page of the e-CRF.

In case the e-CRF is unavailable when the investigator was informed of the ERIN, he/she should:

- **Immediately** fill in a paper “Adverse event” page:
 - For serious event on a paper “Adverse event – Initial information” page.
 - For event initially non-serious on a paper “Adverse event – Initial information” page, and the worsening leading to seriousness on a paper “Adverse event – Additional information” page.
- Immediately send the page(s) by fax or a scan of them by e-mail to the person(s) designated in the contact details provided in the investigator's study file or outside working hours, the 24-hour phone line.
- As soon as the e-CRF becomes available, the investigator should enter these data in the “Adverse Event” page of the e-CRF.

8.9.3. Responsibilities of the sponsor

In accordance with international guidance, the assessment of the seriousness and the causality of adverse events are usually made by the investigator but falls also under sponsor's duties, who is responsible for ensuring that all suspected unexpected serious adverse reactions are reported to Competent Authorities and Ethics Committees.

The sponsor will review the seriousness of the adverse events and the causality of (at least) the serious adverse events, whether reported by the investigator or upgraded by the sponsor. The causality and the seriousness may be upgraded (but never downgraded). Anonymized copies of relevant documents may be asked for the event assessment. If the assessments of the investigator and the sponsor are different, both will be reported in the clinical study report.

In addition, the sponsor is responsible for determining whether an AE is **expected or unexpected**. An AE will be considered unexpected if the nature, severity, or frequency of the event is not consistent with the risk information previously described for the IMP.

Independently of the regulatory obligations of the investigator, the sponsor must report the pharmacovigilance data and any new safety finding likely to affect the benefit /risk balance of the product, required in ICH GCP guidelines and local regulations, to the appropriate Authorities, to all the investigators involved and to the trial participants involved - through the investigators - as mentioned in [Section 13.4](#).

The concerned authorities will be notified as soon as possible by the sponsor of the DMC recommendations if any, where relevant for the safety of subjects (*i.e.* modification or termination of the study).

8.10. Responsibilities of Data Monitoring Committee

In accordance with the DMC charter and the rules for DMC functioning, the DMC is responsible for reviewing the efficacy (including disease-related events) and safety data on a regular basis and providing written recommendations to the International Coordinator and the sponsor regarding the conduct of the study (modification or termination). For more detail refer to [Section 12.4](#).

8.11. Management of treatment dose adaptations due to toxicities

For participants who have experienced a dosing modification, reasons for dose modifications or delays, the supportive measures taken, and the outcome will be documented in the participant's source documents and recorded in the e-CRF.

In the futuximab/modotuximab plus trifluridine/tipiracil arm doses of either futuximab/modotuximab, or trifluridine/tipiracil, or both drugs can be modified, depending on the toxicity observed.

General rules:

Before starting a new treatment cycle, toxicity must have resolved as specified in the [Sections 8.11.1](#) and [8.11.2](#) and the safety criteria to be met as specified in the [Section 6.1.5](#).

- If toxicity due to any of the IMPs does not resolve during the given cycle to Grade 1 or baseline, the start of the next cycle will be delayed for a maximum of 30 days for trifluridine/tipiracil and 21 days for futuximab/modotuximab (see [Sections 8.11.1](#) and [8.11.2](#)). If more than the maximum delay period is needed for recovery, the next cycle should be started with the IMP not concerned by the toxicity.
- If, in the opinion of the investigator, the toxicity is clearly related to one of the treatments, reduction of one and not the other agent is appropriate. If, in the opinion of the investigator, the toxicity is related to the futuximab/modotuximab only futuximab/modotuximab should be reduced according to recommended dose modifications. If, in the opinion of the investigator, the toxicity is related to the trifluridine/tipiracil only trifluridine/tipiracil should

be reduced according to recommended dose modifications. If the toxicity is related to the combination of two agents, both agents should be reduced (if applicable), interrupted or discontinued according to the recommended dose modifications.

- Participants may have trifluridine/tipiracil discontinued and continue on futuximab/modotuximab alone. Similarly, participants may discontinue futuximab/modotuximab and continue on trifluridine/tipiracil alone if appropriate.

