6.1.5. Retreatment criteria

These criteria are applicable after any dose delay and before the start of each cycle:

- ANC $\geq 1.5 \times 10^9/L$.
- Platelets $\geq 75 \times 10^9/L$.
- Ongoing AEs (IMP-related) should NOT meet study discontinuation criteria.
- Ongoing AEs (IMP-related) should have either ameliorated to \leq Grade 1 severity, returned to baseline status, or resolved, with the exceptions of Grade 2 clinical events that are being adequately controlled with best supportive care (e.g. nausea, vomiting, diarrhoea, fatigue, rash) and asymptomatic laboratory abnormalities that are considered clinically insignificant and uncomplicated or that are resolving spontaneously or with conventional medical interventions.
- Ongoing AEs which, in the opinion of the investigator, should make it advisable to delay the administration of treatments.

Note: Safety criteria to be met prior to the start of each cycle could be in accordance with the local SmPC of trifluridine/tipiracil.

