8.11.2.2. Dose Delay

Toxicities may be managed by delay in dosing, provided they do not meet the criteria for IMP discontinuation ([Section 5.8.1](#)). In such cases, the period between any 2 scheduled doses may be extended up to 3 days (inclusive) to allow an improvement of the toxicity. Such delays will be considered an extension within the current cycle. If a delay of more than 3 days from the scheduled dose date is necessary, the dose should be omitted and proceed to the next scheduled dose (i.e. 14 days from the last dose).

If 3 consecutive doses are needed to be omitted (i.e. more than 21 days from the last dose of futuximab/modotuximab), the participant should be discontinued from futuximab/modotuximab. All delays of futuximab/modotuximab must be documented on the appropriate page of the participant's e-CRF.

If toxicity does not resolve during the given cycle to Grade 1 or baseline, the start of the next cycle may be delayed by a maximum of 21 days from the last dose of futuximab/modotuximab administered to allow the initiation of both IMPs at the same time in the next cycle. If more than 21 days from the last dose administered are needed for recovery, futuximab/modotuximab should be discontinued and the next cycle will start with only trifluridine/tipiracil.

Dosing may be restarted at the same dose, as clinically indicated. However, administration of futuximab/modotuximab may only be restarted provided retreatment criteria are met ([Section 6.1.5](#)).

For treatment restart with no dose reduction:

- If treatment restart after the omission of 1 dose (i.e. treatment delay up to 14 days from the last dose), it is recommended that dosing restart with maintenance dose of 6 mg/kg;
- If treatment restart after the omission of 2 consecutive doses (i.e. treatment delay up to 21 days from the last dose), it is recommended that dosing re-start with the re-administration of a loading dose of 9 mg/kg followed by weekly maintenance doses of 6 mg/kg.

For treatment restart with dose reduction, see Section 8.11.2.3.

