8.11.2.3. Dose Reduction

In the event of Grade 3 treatment-related AEs, the participant may continue on study if there is evidence of clinical benefit as judged by the treating physician, but could do so at a reduced dose of futuximab/modotuximab once retreatment criteria are met ([Section 6.1.5](#)) (specific instructions for dose reduction linked to IRR, dermatologic AEs, and hypomagnesemia, are provided in Appendices 9, 10 and 11, respectively). All dose reductions of futuximab/modotuximab must be documented on the appropriate page of the participant's e-CRF.

If toxicity is to be managed by dose reduction, the futuximab/modotuximab dose will be decreased as shown in ([Table \(8.11.2.3\) 1](#)). Dose reduction may occur either during treatment cycles, or between cycles, as clinically indicated.

Table (8.11.2.3) 1 - Dose reduction of futuximab/modotuximab

Starting dose (Dose level 0)	Dose level -1	Dose level -2
Futuximab/modotuximab*	6 mg/kg	4.5 mg/kg

*Note: Dose Reductions for 9 mg/kg loading dose not applicable. The number of dose reductions allowed is limited to 2

Abbreviations (in alphabetical order): kg, kilogram; mg, milligram

A maximum of 2 dose reductions for futuximab/modotuximab-related toxicity are allowed (to a minimum dose of 3 mg/kg). Do not re-escalate dose after it has been reduced.

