Appendix 10: Management of Dermatologic Adverse Events

A. Grading and Management of futuximab/modotuximab-Related Dermatologic AEs

Recommendations for management of Grade 1 to Grade 3 futuximab/modotuximab-induced dermatologic AEs (*i.e.*, rash, xerosis, paronychia, pruritus, photosensitivity, and fissures) are summarized below. If a patient experiences any Grade 4 dermatologic AE, the patient must be withdrawn from futuximab/modotuximab treatment. It is strongly recommended that a dermatologist is consulted in the event of Grade 3 or Grade 4 dermatologic AE.

Futuximab/modotuximab - Management of Rash			
NCI-CTCAE Grade	Action with futuximab/modotuximab	Treatment- Rash	
1	Papules and/or pustules covering < 10% body surface area (BSA) , which may or may not be associated with symptoms of pruritus or tenderness	Continue at the same dose	Topical : Face and Chest Steroid creams of low potency; alclometasone 0.05% or desonide 0.05% or fluocinolone 0.01%; 2 x daily Topical : Rest-of-body moisturizers; 2 x daily Systemic ¹ : minocycline 100 mg/day or doxycycline 200 mg/day; for at least 4 weeks
2	Papules and/or pustules covering 10-30% BSA , which may or may not be associated with symptoms of pruritus or tenderness; associated with psychosocial impact; limiting instrumental activities of daily living (ADL); papules and/or pustules covering > 30% BSA with or without mild symptoms	Continue at the same dose If locally debilitating for the patient, consider following guidelines for dose-delay and dose reduction as outlined in the Dose Reduction for Grade 3 Dermatologic AEs table in Section B below	Topical : See Grade 1 Systemic ¹ : 
 - minocycline 100 mg/day or doxycycline 200 mg/day; for at least 4 weeks - 1 week course of oral steroid: methylprednisolone 4 mg tablets: 
 • Day 1: 2-1-1-2 • Day 2: 1-1-1-2 • Day 3: 1-1-1-1 • Day 4: 1-1-1 • Day 5: 1-0-1 • Day 6: 1
3	Papules and/or pustules covering > 30% BSA , with moderate or severe symptoms; limiting selfcare ADL; IV antibiotics indicated	Delay dose of futuximab/modotuximab, continue skin treatment and re-assess. Refer to the Dose Reduction for Grade 3 Dermatologic AEs table in Section B below for further guidelines on dose reduction	Topical : See Grade 1 Systemic ¹ : See Grade 2

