NCI-CTCAE Grade	Action with futuximab/modotuximab	Treatment- Fissures
1	Initiated at first occurrence	No action Topical: - thick moisturizers of zinc oxide (13-40%) cream - liquid glues of cyanoacrylate to seal cracks
2	If no improvement after 2 weeks from initiation of Step 1	No action Topical: - thick moisturizers of zinc oxide (13-40%) cream under occlusion at night - salicylic acid 6% cream or ammonium lactate/lactic acid 12%
3	If no improvement after 2 weeks from initiation of Step 2	Delay dose of futuximab/modotuximab, and re-assess. Discuss need for dose reduction and/or further dose omissions with sponsor or designee Continue local treatment as described in Step 2

Prophylaxis for fissures includes careful use of moisturizing creams and/or ointments 3 times a day and after handwashing, using only fragrance-free soaps. Should fissures begin to form, a stepwise approach outlined above should be followed. **Topical application of cyanoacrylate tissue adhesive (i.e., surgical glue) products may be considered to promote wound repair.**

If fissures occur which are unresponsive to intensive therapeutic treatment as specified above, futuximab/modotuximab dosing should be delayed. The need for dose-reduction and/or continued dose-delays should be discussed with the sponsor or designee, if adequate improvement is not seen after the initial dose-delay.

B. Dose Reduction Guidelines for futuximab/modotuximab-Related Dermatologic AEs

Dose delay and/or intrapatient dose reduction(s) will be required upon occurrence of Grade 3 anti-EGFR associated dermatologic AE, and should be implemented according to Table Dose Reduction for Grade 3 Dermatologic AEs

Futuximab/modotuximab Dose Reduction for Grade 3 Dermatologic AEs			
Dermatologic AE Grade 3	Futuximab/modotuximab Immediate Action	Outcome Improvement	Futuximab/modotuximab
First occurrence	Delay dose	Grade \leq 1	Continue at same dose
		Grade 2	Reduce to 4.5 mg/kg
		No improvement	Discontinue
Second occurrence	Delay dose	Grade \leq 1	Continue at same dose
		Grade 2	At dose of 6.0 mg/kg: Reduce to 4.5 mg/kg At dose of 4.5 mg/kg: Reduce to 3.0 mg/kg
		No improvement	Discontinue
Third occurrence	Delay dose	Grade \leq 1	Continue at same dose
		Grade 2	At dose of 6.0 mg/kg: Reduce to 4.5 mg/kg At dose of 4.5 mg/kg: Reduce to 3.0 mg/kg At dose of 3.0 mg/kg: discontinue
		No improvement	Discontinue
Fourth occurrence	Discontinue	Any	Discontinue

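### At cycle start, Sections 8.11 and 8.11.2.2 use a Grade 1-or-baseline threshold that Sections 6.1.5, 8.12.5 and Appendix 10 do not require for a controlled Grade 2 skin event, and no rule says which prevails

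*Protocol*

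**What the plan says.** Two groups of text govern the same moment, the due date of a new cycle.

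**Text that asks for Grade 1 or baseline**
- Protocol 8.11, first general rule: if toxicity due to either investigational drug "does not resolve during the given cycle to Grade 1 or baseline, the start of the next cycle will be delayed". The maximum is 30 days for trifluridine/tipiracil and 21 days for futuximab/modotuximab. No Grade 2 or skin exception is given. The sentence before it asks for resolution as set out in 8.11.1 and 8.11.2 "and the safety criteria to be met as specified in the" section on retreatment criteria, 6.1.5.
- Protocol 8.11.2.2 repeats the threshold for the antibody, but says the next cycle *may* be delayed. It then adds: "If more than 21 days from the last dose administered are needed for recovery, futuximab/modotuximab should be discontinued and the next cycle will start" with trifluridine/tipiracil alone.

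**Text that allows dosing at Grade 2**
- Protocol 6.1.5 sets its own scope: "These criteria are applicable after any dose delay and before the start of each cycle". Its recovery requirement is Grade 1, baseline or resolved, "with the exceptions of Grade 2 clinical events that are being adequately controlled with best supportive care (e.g. nausea, vomiting, diarrhoea, fatigue, rash").
- Protocol 8.12.5 requires delay or reduction for Grade 3 skin events. For Grade 2 it makes them optional, and only when the reaction is debilitating.
- Protocol 8.11.2.3: after a Grade 3 event the participant "could do so at a reduced dose of futuximab/modotuximab once retreatment criteria are met", with Appendix 10 named as the specific guidance on dose reduction for skin events.
- Appendix 10 A, Grade 2 rash: "Continue at the same dose If locally debilitating for the patient, consider following guidelines for dose-delay and dose reduction". Appendix 10 B, first Grade 3 event that has improved to Grade 2: "Reduce to 4.5 mg/kg".

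**The concern.** A site with a participant whose rash is Grade 2 and controlled on the day Cycle 2 is due can find support for two different actions. Section 8.11 read literally holds both drugs. Section 6.1.5 and Appendix 10 let the cycle start on time.

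The situation is foreseeable. Protocol 2.8 reports dermatological toxicity of any grade in 78 of 84 participants (93%) on the same 9/6 mg/kg regimen.

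The choice also reaches an endpoint. Table (3.4) 1 makes adverse events that lead to interruption, modification, delay or permanent stop of treatment part of the primary Safety Lead-In assessment. If sites resolve the ambiguity differently, that count partly reflects which section was followed and not only how well the combination is tolerated.

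**Working it through.** **1. Does *or baseline* remove the conflict?** For rash, no. Exclusion criterion 35a bars rash above Grade 1 from prior anti-EGFR therapy at entry. Criterion 23a also bars unrecovered non-haematologic toxicity of Grade 2 or more from earlier anticancer therapy, with some exceptions. An on-study Grade 2 rash is therefore normally above baseline.

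**2. Can both rules be applied together?** Section 8.11 joins its own resolution condition to 6.1.5 with *and*. If both must be met, the Grade 2 exception in 6.1.5 has no effect at cycle start, although 6.1.5 says it applies there. Appendix 10 A would still be contradicted. If 6.1.5 is enough, the first general rule of 8.11 is wrong as written.

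**3. Timing for a Grade 2 rash present at C2D1, with no earlier omission**
- Antibody doses fall on days 1, 8, 15 and 22, and Cycle 2 is due on day 29.
- The limit in 8.11.2.2 runs from the last dose: 22 + 21 = day 43.
- Under 6.1.5 and Appendix 10 A, Cycle 2 starts on day 29. Under 8.11 it can slip by up to 43 − 29 = 14 days. Beyond day 43, 8.11.2.2 discontinues the antibody.

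**4. Effect on Cycle 1 relative dose intensity**

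SAP 5.2.1.4 measures a cycle from its first intake to the first intake of the next cycle. It defines dose intensity as cumulative dose divided by cycle duration in weeks, and relative dose intensity as that figure over the planned intensity.
- Planned, trifluridine/tipiracil: 70 × 10 / 4 = 175 mg/m²/week (700 mg/m² over the cycle).
- Planned, antibody in Cycle 1: (9 + 3 × 6) / 4 = 27 / 4 = 6.75 mg/kg/week.

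| Start of Cycle 2 | Cycle 1 length | Trifluridine/tipiracil | Antibody | Relative dose intensity |
|---|---|---|---|---|
| Day 29 | 4 weeks | 700/4 = 175 | 27/4 = 6.75 | 100% |
| Day 36 (1-week delay) | 5 weeks | 700/5 = 140 | 27/5 = 5.4 | 28/35 = 80.0% |
| Day 43 (2-week delay) | 6 weeks | 700/6 = 116.7 | 27/6 = 4.5 | 28/42 = 66.7% |

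The loss is the same for both drugs because 8.11 delays the cycle, not one agent.

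**5. How many participants?** The protocol gives skin events of any grade only. The share at Grade 2 on a cycle due date is not reported, so no count follows from the documents.

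**The case against.** The strongest defence is that the skin-specific text points one way. Sections 6.1.5, 8.11.2.3 and 8.12.5 and both parts of Appendix 10 allow treatment at Grade 2, and against them stands one general rule written for all toxicities of both drugs. Section 8.11.2.2 says *may*, and it sends restart of the antibody to 6.1.5 in a sentence that follows its cycle-start paragraph and is not limited to dosing within a cycle. Only 8.11.1 says toxicity *must* have returned to Grade 1 or baseline, and only for trifluridine/tipiracil.

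Much of this stands. A reader might infer two flatly opposite mandatory instructions; the documents do not support that, because the mandatory delay comes from 8.11 alone. What does not stand is the claim that the antibody section sets no such threshold. Section 8.11.2.2 states Grade 1 or baseline for the next cycle, and its discontinuation sentence follows directly from it. Section 8.11.2.3 calls Appendix 10 specific for dose reduction, not for overriding the delay or stop rule.

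Three further inferences are not supported:
- *That Appendix 10 B permits delay without limit.* Its note on longer delays refers to the two-week reassessment, and 8.11.2.2 already discontinues the antibody beyond 21 days from the last dose. The note only fails to say so.
- *That a relative dose intensity of 66.7% breaches the 75% needed for DLT evaluability.* Section 4.1.3.2 compares administered with planned milligrams, not dose per week. A late Cycle 2 leaves that ratio unchanged.
- *That a dose figure can be fixed for a Grade 3 event that falls to Grade 2.* If C1D22 is omitted and dosing resumes on day 36 at 4.5 mg/kg, 21 mg/kg has been given of 27 + 24 = 51 planned over two cycles. Three remaining doses on the original calendar give 34.5/51 = 67.6%; a full four-dose Cycle 2 from day 36 gives 39/51 = 76.5%. The result depends on the convention, so it is not relied on here.

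**Conclusion.** The concern holds as an unreconciled threshold at cycle start. A site that follows 8.11 to the letter would withhold both drugs for an event that Appendix 10 says to treat through. For one such participant that means a Cycle 1 relative dose intensity of 80.0% or 66.7% instead of 100%, and possible loss of the antibody after day 43. These figures assume all Cycle 1 doses were given and the event stays at Grade 2 throughout the delay.

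The consequence is for exposure and for the primary Safety Lead-In count of events leading to delay or permanent stop. A reader might extend it to unequal trifluridine/tipiracil exposure between randomised arms, but the SAP introduction states that the Randomised part was cancelled, so the reach is about 25 participants. Sample size and power are not affected. The correction is worth making because it is small and adopts the threshold that most of the protocol already uses.

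**What to change.** - In the first general rule of 8.11 and in 8.11.2.2, for futuximab/modotuximab toxicities, replace *to Grade 1 or baseline* with *to the retreatment criteria in Section 6.1.5*.
- Leave the trifluridine/tipiracil rule in 8.11.1 unchanged. The general rule in 8.11 covers both drugs, so it needs to state the two thresholds separately.
- Add to the note under the Appendix 10 B table that longer delays remain subject to the 21-day limit in 8.11.2.2.

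Make no change to the investigator's discretion over debilitating Grade 2 events or to the meaning of the *No improvement* row. Either would be new dosing policy, not harmonisation.

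The cost is one phrase in each of two sections and one sentence in an appendix note, with no change to data collection or analysis. If the sponsor classes the change as a substantial amendment, Section 17.1.2 requires ethics committee opinion and submission to the competent authorities.
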